7.4. Injection Site Assessments

Injection site assessments will be performed immediately and 1 hour after administration of each dose of study drug (see [Table 1](#) and [Table 2](#)). The injection site(s) will be assessed for erythema, induration, ecchymosis, and pain, and severity will be graded according to the following criteria:

- Injection-site erythema, injection-site induration, and injection-site ecchymosis will be graded according to measurements: absent, 5 mm to ≤ 50 mm (mild), >50 to ≤ 100 mm (moderate), and >100 mm (severe). Induration must be assessed by careful superficial palpation avoiding pressuring or squeezing the injection site.
- Injection-site pain will be graded as: 0 = no pain, 1 = mild, 2 = moderate, 3 = severe, 4 = worst possible.

If a patient has severe injection site induration, erythema, and/or ecchymosis and/or grade 3 (severe) or grade 4 (worst possible) injection site pain at 1 hour after completion of study drug administration, the patient will be reassessed at 3 hours after study drug administration and hourly thereafter until the reaction/pain is of moderate or less severity.

Number (%) of patients having injections at each visit and their post injection assessments for erythema, induration, ecchymosis, and pain of each grade will be summarized by visit and timepoint for each treatment group. If a patient has multiple sites with different severities, the most severe reaction will be summarized.

To differentiate between assessments at active treatment (TEV-48125) injection sites and placebo injection sites for subjects who receive combined injections of TEV-48125 225 mg and

placebo at the same dose, ie, loading dose of TEV-48125 at 675 mg followed by monthly TEV-48125 at 225 mg, and 225 mg TEV-48125 (1 active, 2 placebo injections) at visit 2, 5, 8, and 11, summaries will be presented by treatment type (TEV-48125 or placebo) within each treatment group. Subjects are only counted once for each treatment type, and if multiple sites with the same treatment type (TEV-48125 or placebo) present with different severities, the most severe reaction will be summarized.

To compare the post injection site assessment between the active TEV-48125 injections and placebo injections, the total number of injections for both active and placebo type will be counted. The number (%) of injection sites fell into different grade of severity will be presented by visits/months.

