At the time of each study visit, the IRT will be queried, and site personnel will retrieve and administer 1.5 mL from each syringe contained in the appropriately numbered kit(s). Kit numbers will be entered into the CRF.

The recommended sc injection sites follow the National Institutes of Health Patient Education Guidelines of June 2012, which are available in [Appendix C](#) of this document and at the following website: http://www.cc.nih.gov/ccc/patient_education/pepubs/subq.pdf. The suggested sites of injection are back of upper arms, lower abdomen/belly/waistline, and front of thighs. At each visit, the injections should be given in a different location (eg, not in precisely the same place), and study staff member(s) responsible for administration of injections should inspect previous injection sites to ensure that they are free of bruising and tenderness and that proper rotation of sites is performed.

Study drug should be removed from the refrigerator and allowed to equilibrate at room temperature for 15 to 30 minutes before study drug administration.

A 1.5-mL volume from each syringe in each visit's kit(s) must be injected sc for dosing to be considered complete. The total number of sc injections and their locations will be recorded for each dosing visit.

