7.2. Study Drug Administration

Patients rolling over from the pivotal efficacy studies who were randomized to the active treatment groups will continue receiving the same treatment (ie, monthly TEV-48125 at 225 mg or quarterly TEV-48125 at 675 mg) throughout this long-term safety and efficacy study. Patients rolling over from the pivotal efficacy studies who received placebo and the new patients will be randomly assigned in a 1:1 ratio using IRT as follows:

- Patients with CM will receive sc TEV-48125 at 675 mg (loading dose) followed by 11 monthly sc doses of TEV-48125 at 225 mg or sc TEV-48125 at 675 mg once every 3 months for 12 months for a total of 4 doses.
- Patients with EM will receive monthly sc TEV-48125 at 225 mg for 12 months or sc TEV-48125 at 675 mg once every 3 months for 12 months for a total of 4 doses

Study drug will be administered as sc injections approximately every 4 weeks (28 days).

In order to maintain the study blind, all patients will receive 3 injections at visits 2, 5, 8, and 11 and 1 injection at all other visits as detailed in [Table 5](#).

Table 5: Study Drug Administration by Treatment Group and Visit

Treatment group in this study	Visit 2	Visits 5, 8, and 11	Visits 3, 4, 6, 7, 9, 10, 12, and 13
Loading dose of TEV-48125 at 675 mg followed by monthly TEV-48125 at 225 mg	3 active injections (225 mg/1.5 mL)	1 active injection (225 mg/1.5 mL) and two 1.5-mL placebo injections	1 active injection (225 mg/1.5 mL)
Monthly TEV-48125 at 225 mg	1 active injection (225 mg/1.5 mL) and two 1.5-mL placebo injections	1 active injection (225 mg/1.5 mL) and two 1.5-mL placebo injections	1 active injection (225 mg/1.5 mL)
Quarterly TEV-48125 at 675 mg	3 active injections (225 mg/1.5 mL)	3 active injections (225 mg/1.5 mL)	one 1.5-mL placebo injection

Duration of treatment (days treated) is the number of days on treatment based on the first and EOT visit day/early withdrawal day (EOT visit day – first day of study drug + 1). For subjects who are lost to follow-up, the last day is defined as the last study drug administration date +27.

Number (%) of patients receiving ≥ 1 dose, ≥ 2 doses, ≥ 3 doses, and so on will be summarized using descriptive statistics by treatment group. Duration of treatment (days) and number of doses will also be summarized using descriptive statistics for each treatment group.

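### The patient-level injection-site summary in SAP 7.4 sets the worst of two placebo sites against one active site, which overstates placebo reactions, and the per-injection table beside it does not state its grouping

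*SAP*

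**What the plan says.** SAP Table 5 (section 7.2) fixes the number of sites. The monthly arm receives "1 active injection (225 mg/1.5 mL) and two 1.5-mL placebo injections" at visits 2, 5, 8 and 11. The loading-dose arm has the same pattern at visits 5, 8 and 11, but three active injections and no placebo at visit 2. The quarterly arm has three active injections at visits 2, 5, 8 and 11. At the other eight dosing visits everyone has one injection: active in the monthly and loading-dose arms, placebo in the quarterly arm.

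SAP 7.4 then plans two displays that separate active from placebo.

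- **Patient level.** To tell the two types apart in patients given both, "summaries will be presented by treatment type (TEV-48125 or placebo) within each treatment group". The rule is "Subjects are only counted once for each treatment type, and if multiple sites with the same treatment type" "present with different severities, the most severe reaction will be summarized" (the parenthesis naming the types is omitted here between the two quotes). The sentence applies this to the loading-dose and monthly arms together: "1 active, 2 placebo injections) at visit 2, 5, 8, and 11".
- **Injection level.** For the stated purpose of comparing active with placebo injections, "the total number of injections for both active and placebo type will be counted", and the number and percentage of sites in each severity grade are given by visit or month. No worst-site rule applies here, and the sentence names no treatment grouping.

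SAP 7.1 sets the general layout for safety summaries: by treatment group as actually received, and overall. SAP 4.4 rules out inferential analysis.

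**The concern.** Local tolerability is one of the primary safety endpoints in the Protocol synopsis, and Protocol 1.4.1.1 lists injection-site erythema and pain among the identified risks. Protocol 3.9 describes the study as uncontrolled, so the placebo injections used for blinding are its only concurrent placebo reference.

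In the patient-level display the two types have unequal chances to show a reaction: two sites for placebo, one for active. If the products were identical, placebo would look worse. The error runs in one direction, in favour of the drug. That the analysis is descriptive does not remove it, because readers will compare adjacent lines of the same table. This is also the only by-type display that SAP 7.4 itself places within treatment group.

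**Working it through.** **Inputs.** Two placebo sites and one active site per patient at the mixed visits (SAP Table 5). The documents state no reaction rate or within-patient correlation, so the values of p and ρ below are assumptions shown over a range. There is no figure in the plan to reproduce.

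**Formula.** Let p be the chance of a reaction (of any grade, or above any chosen grade) at one placebo site, and ρ the correlation between a patient's two placebo sites. Then

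P(both) = p² + ρp(1 − p), and P(at least one of two) = 2p − [p² + ρp(1 − p)].

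The active line stays at its per-site rate.

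**Equal products, p = 20% for both types.** Here p² = 0.04 and p(1 − p) = 0.16.

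- ρ = 0: 0.40 − 0.04 = 36.0%
- ρ = 0.5: 0.40 − (0.04 + 0.08) = 28.0%
- ρ = 0.9: 0.40 − (0.04 + 0.144) = 21.6%
- ρ = 1: 0.40 − 0.20 = 20.0%

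Active shows 20% throughout. The inflation ratio at ρ = 0 is 0.36/0.20 = 1.8. It is 1.95 at p = 5% (9.75%) and 1.99 at p = 1% (1.99%). At ρ = 1 there is none.

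**A true active excess: 10% placebo, 15% active per site.** Placebo in the patient-level table is 0.20 − (0.01 + 0.09ρ) = 0.19 − 0.09ρ.

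| ρ | Placebo shown | Active shown | Difference shown (points) | True difference (points) |
|---|---|---|---|---|
| 0 | 19.0% | 15% | −4.0 | +5.0 |
| 0.3 | 16.3% | 15% | −1.3 | +5.0 |
| 0.5 | 14.5% | 15% | +0.5 | +5.0 |
| 0.9 | 10.9% | 15% | +4.1 | +5.0 |
| 1 | 10.0% | 15% | +5.0 | +5.0 |

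The sign reverses when 0.19 − 0.09ρ > 0.15, that is for ρ below 0.04/0.09 = 0.44. A simulation of 1,000,000 patients gave placebo rates of 19.0% at ρ = 0 and 14.5% at ρ = 0.5, as the formula does.

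**Per-injection table, same patients.** Each type's percentage is its own per-site rate, here 10% and 15%, so the difference is +5.0 points at any ρ. There is no inflation.

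**Per-injection table, if arms are pooled.** At visits 5, 8 and 11 a quarterly patient supplies three active sites and no placebo site; a monthly or loading-dose patient supplies one active and two placebo. If a fraction q of patients is quarterly, the share of active sites from quarterly patients is 3q/[3q + (1 − q)] = 3q/(1 + 2q). The documents do not give q. Assumed values of 0.4, 0.5 and 0.6 give 1.2/1.8 = 67%, 1.5/2.0 = 75% and 1.8/2.2 = 82%. In a pooled column, most active sites would then come from patients with no placebo site.

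**The case against.** The strongest reply is that the patient-level table is not the SAP's comparison. It is introduced as a way to tell the two injection types apart; the next paragraph makes the comparison, per injection and without a worst-site rule. This stands. A reader might infer that the plan as a whole hides an active excess, and the documents do not support that.

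Three further inferences also go too far.

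- **That the per-injection table pools arms.** SAP 7.4 is silent on this, and the default in SAP 7.1 points to display by treatment group plus overall. If that default applies, the active and placebo percentages for the monthly arm at its mixed visits come from the same patients at the same visit. With complete assessments, their difference equals the mean within-patient difference. The gap is then a missing statement of layout and an interval that allows for clustering.
- **That no other fair placebo comparison exists.** At the eight single-injection visits, one active site in monthly-regimen patients can be set against one placebo site in quarterly patients. New and placebo-rollover patients were randomised 1:1 between these regimens (SAP 2.4.1), and SAP 7.1 separates them from active rollovers.
- **That sites cannot be traced to syringes.** Protocol 5.1 says "The total number of sc injections and their locations will be recorded for each dosing visit" and that kit numbers go into the CRF, with one syringe per kit. It does not spell out the link between the two, but the CRF is not among the documents, and planning summaries by type presupposes a link.

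The sizes above are also assumed, and highly correlated sites would leave little inflation. The visit 2 wording has a defence as well: the sentence is limited to patients who receive both types at the same dose. None of this removes the asymmetry in the patient-level table.

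**Conclusion.** The point holds for one display. In the patient-level by-type summary, the placebo rate is overstated for the monthly arm at visits 2, 5, 8 and 11 and for the loading-dose arm at visits 5, 8 and 11, unless a patient's two placebo sites always agree. Under the assumed rates the overstatement runs from nothing at perfect correlation to nearly twofold at independence, and at low to moderate correlation it can reverse a true 5-point excess. The quarterly arm, the loading-dose arm at visit 2 and the single-injection visits are not affected.

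The per-injection table gives uninflated rates, so the remaining risk is that two displays of one primary tolerability endpoint disagree without explanation, and that the sound one is weakened if read only in a pooled column. The defect is real but contained, and should be corrected in the SAP.

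**What to change.** In SAP 7.4:

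1. For patients with mixed injections at a visit, report the active-site rate, the mean rate over the two placebo sites, and their within-patient difference, in place of or beside the worst-per-type count. A descriptive confidence interval clustered by patient is optional; SAP 6.4.2.1 already gives intervals without testing.
2. If the patient count is kept, footnote that its active and placebo columns rest on unequal numbers of sites.
3. State that the per-injection table is given by treatment group as well as overall.
4. Reword the visit list so that it agrees with Table 5, which shows no placebo injection for the loading-dose arm at visit 2.

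The cost is SAP wording and one extra or changed table. Keeping the patient count beside the per-site rates preserves patient-level incidence by type. No new data collection is proposed.

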7.5. Deaths

If any patient dies during the study, all relevant information will be discussed in the patient's narratives included in CSR.

7.6. Clinical Laboratory Tests

Clinical laboratory tests (serum chemistry, hematology, coagulation, and urinalysis) will be performed at the time points detailed in [Table 1](#) and [Table 2](#) using the central laboratory. Specific laboratory tests to be performed are listed below in [Table 6](#).

Table 6: Clinical Laboratory Test

Serum chemistry	Hematology	Coagulation	Urinalysis

 • calcium • phosphorus • sodium • potassium • chloride • carbon dioxide • magnesium • glucose • blood urea nitrogen • creatinine • ALT • AST • total bilirubin • direct bilirubin • indirect bilirubin (calculated) • lactate dehydrogenase • GGT • ALP • albumin • creatine phosphokinase • total protein 	
 • hemoglobin • hematocrit • RBC count • RBC indices 
 - mean corpuscular volume - mean corpuscular hemoglobin concentration - RBC distribution width • platelet count • WBC count and differential count (absolute values and percentages) 
 - neutrophils - lymphocytes - eosinophils - monocytes - basophils 	
 • prothrombin time • partial thromboplastin time • INR 	
 • color and appearance • specific gravity • pH • blood (hemoglobin) • glucose • albumin • protein • ketones • leukocyte esterase • nitrite • direct bilirubin • microscopic 
 - bacteria - RBCs - WBCs - casts - crystals

Laboratory tests results and changes from baseline for chemistry, hematology, urinalysis, and coagulation laboratory tests will be summarized by visits for each treatment group using descriptive statistics. Shifts (below, within, and above the normal range) from baseline to each visit and endpoint will be summarized using patient counts.

The incidence of potentially clinically significant abnormal results will be summarized using descriptive statistics with the criteria specified in [Table 7](#). The potentially clinically significant abnormal laboratory values will include all postbaseline values (including scheduled, unscheduled, and early termination visits) for the summaries. Listings of patients who have potentially clinically significant abnormal laboratory data will be presented.

Table 7: Criteria for Potentially Clinically Significant Laboratory Values

Test	Criterion value
Serum chemistry	
ALT	$\geq 3 \times \text{ULN}$
AST	$\geq 3 \times \text{ULN}$
ALP	$\geq 3 \times \text{ULN}$
GGT	$\geq 3 \times \text{ULN}$
Lactate dehydrogenase	$\geq 3 \times \text{ULN}$
Blood urea nitrogen	$\geq 10.71 \text{ mmol/L}$
Creatinine	$\geq 177 \mu\text{mol/L}$
Uric acid Men	$\geq 625 \mu\text{mol/L}$
Women	$\geq 506 \mu\text{mol/L}$
Bilirubin (total)	$\geq 34.2 \mu\text{mol/L}$
Hematology	
Hematocrit Men	$< 0.37 \text{ L/L}$
Women	$< 0.32 \text{ L/L}$
Hemoglobin Men	$\leq 115 \text{ g/L}$
Women	$\leq 95 \text{ g/L}$
WBC counts	$\leq 3 \times 10^9/\text{L}$ or $\geq 20 \times 10^9/\text{L}$
Eosinophils	$\geq 10\%$
Absolute neutrophil counts	$\leq 1 \times 10^9/\text{L}$
Platelet counts	$\leq 75 \times 10^9/\text{L}$ or $\geq 700 \times 10^9/\text{L}$
Urinalysis	
Blood (HGB)	≥ 2 unit increase from baseline
Glucose	≥ 2 unit increase from baseline
Ketones	≥ 2 unit increase from baseline
Total protein	≥ 2 unit increase from baseline

ALP=alkaline phosphatase; ALT=alanine aminotransferase; AST=aspartate aminotransferase; GGT=gamma-glutamyl transpeptidase; HGB=hemoglobin; INR=international normalized ratio; ULN=upper limit of normal range; WBC=white blood cell

Serum beta-human chorionic gonadotropin (β -HCG) tests will be performed for all women of childbearing potential at screening (visit 1), and urine β -HCG tests will be performed for women of childbearing potential at visits 2 through 5. Positive pregnancy test results will be listed.

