4. GENERAL ISSUES FOR DATA ANALYSIS

4.1. General

Descriptive statistics for continuous variables include count (n), mean, standard deviation (SD), standard error (SE), median, minimum, and maximum. Descriptive statistics for categorical variables include patient counts and percentages.

Summaries of potentially clinically significant abnormal values will include all postbaseline values (including scheduled, unscheduled, and early termination visits).

Endpoint for safety analyses and summaries is the last observed postbaseline data (see Section 4.6 for the definition).

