4.2. Specification of Baseline Values

For the patients rolling over from the pivotal efficacy studies, their baseline values will be the baseline values from the pivotal studies.

Eligible new patients will enter a 28-day run-in period during which they will complete daily electronic headache diary entries. The efficacy baseline values are based on the run-in period data. If the run-in period is greater than 28 days, the baseline values will be normalized to 28-day.

The efficacy variable baseline values during the 28-day run-in period that will be derived from the e-diary include

- total number of migraine days
- total headache days of at least moderate severity
- total headache days of any severity
- total number of days of use of any acute headache medication
- total number of headache hours of at least moderate severity
- total number of headache hours of any severity
- total number of days with nausea or vomiting
- total number of days with photophobia and phonophobia

Other efficacy baseline values that will be measured on day 0 include

- disability score in patients with CM, as measured by the HIT-6 ([Appendix C](#))
- disability score in patients with EM, as measured by the MIDAS questionnaire ([Appendix D](#))
- quality of life, as measured by the MSQOL questionnaire ([Appendix E](#))
- health status, as measured by the EQ-5D-5L questionnaire ([Appendix G](#))
- patient depression status, as measured by the PHQ-2 and the PHQ-9 ([Appendix I](#))

- patient work productivity and activity impairment, as measured by the WPAI questionnaire ([Appendix J](#))

For safety data, new patient's baseline values will be the last values prior to the 1st dose of study drug.

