7.7. Vital Signs

Vital signs (pulse, systolic and diastolic blood pressure, body temperature, and respiratory rate) will be measured before other assessments (eg, blood draws and administration of questionnaires) at the time points detailed in [Table 1](#) and [Table 2](#).

For any abnormal vital sign finding, the measurement should be repeated as soon as possible. Any vital sign value that is judged by the investigator as a clinically significant change (worsening) from a baseline value will be considered an adverse event.

Vital signs values and changes from baseline to each visit and endpoint will be summarized using descriptive statistics. The incidence of potentially clinically significant abnormal values will be summarized for selected vital signs using descriptive statistics.

[Table 8](#) specifies the criteria for identifying vital signs as potentially clinically significant abnormal. Note that in order to be identified as potentially clinically significant abnormal, a value would need to meet both conditions below: ie, have a value beyond the criterion value and a change of at least the magnitude specified in the change from baseline column. Summaries of potentially clinically significant abnormal vital signs values will include all postbaseline values (including scheduled, unscheduled, and early termination visits).

Table 8: Criteria for Potentially Clinically Significant Vital Signs

Vital Sign	Criterion value	Change relative to baseline
Pulse	≥ 120 bpm	Increase of ≥ 15 bpm
	≤ 50 bpm	Decrease of ≥ 15 bpm
Systolic blood pressure	≥ 180 mm Hg	Increase of ≥ 20 mm Hg
	≤ 90 mm Hg	Decrease of ≥ 20 mm Hg
Diastolic blood pressure	≥ 105 mm Hg	Increase of ≥ 15 mm Hg
	≤ 50 mm Hg	Decrease of ≥ 15 mm Hg
Respiratory rate	< 10 breaths/min	
Body temperature	$\geq 38.3^\circ\text{C}$	Change of $\geq 1.1^\circ\text{C}$

A listing for clinically significant abnormal vital signs will be presented.

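### For tests without a numeric entry limit, the SAP 7.6 incidence of potentially clinically significant laboratory values includes patients who already met the cut-off before any drug

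*SAP*

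**What the plan says.** SAP 7.6 describes the summary in these terms: "The incidence of potentially clinically significant abnormal results will be summarized using descriptive statistics with the criteria specified in" Table 7. It then fixes which values count: "The potentially clinically significant abnormal laboratory values will include all postbaseline values (including scheduled, unscheduled, and early termination visits) for the summaries". SAP 4.1 gives the same rule for potentially clinically significant (PCS) values in general.

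In Table 7 the chemistry and haematology rows are plain thresholds, for example eosinophils at or above 10%, BUN at or above 10.71 mmol/L, and WBC at or below 3 or at or above 20 × 10⁹/L. The urinalysis rows of the same table are different: each asks for a "unit increase from baseline" of at least 2. For vital signs, SAP 7.7 says that "in order to be identified as potentially clinically significant abnormal, a value would need to meet both conditions below", namely a threshold and a change. Table 8 leaves the change cell empty only for respiratory rate.

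Baseline is before any study drug for everyone. SAP 4.2 says: "For the patients rolling over from the pivotal efficacy studies, their baseline values will be the baseline values from the pivotal studies". For new patients the safety baseline is the last value before dose 1.

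**The concern.** Incidence ordinarily means new occurrence. Under this rule a patient with eosinophils of 11% before the first dose and 11% at any later visit is a case, although nothing has changed. Protocol 3.9 calls the study uncontrolled, and every treated patient receives TEV-48125. The dose groups run in parallel, but no untreated group shows how often such values occur without the drug. Protocol 9.5.1 makes the safety endpoints primary, and SAP 2.5.1 sends an interim data cut into a report supporting a licence application. A percentage that mixes pre-existing with emergent abnormalities could therefore be set beside other safety rates without the means to discount the pre-existing part.

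**Working it through.** **1. The counting rule.** Set side by side:

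| Criteria | Threshold | Baseline condition |
|---|---|---|
| Table 7, chemistry and haematology | yes | none |
| Table 7, urinalysis | not separate | increase of at least 2 units |
| Table 8, vital signs except respiratory rate | yes | change of stated size |
| Table 8, respiratory rate | yes | none |

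Neither SAP 4.1, SAP 7.6 nor Protocol 9.7.2 restricts the laboratory count to patients below the cut-off at baseline, and no at-risk denominator is given. The SAP does not say outright that pre-existing cases are counted. That follows from the rule and from the absence of a baseline condition.

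**2. Which tests are exposed.** Protocol 4.2.2 excludes new patients with ALT, AST or ALP above 1.5 × ULN (after a repeat test). The Table 7 cut-off is 3 × ULN, so a new patient should not enter already meeting it. Creatinine above 1.5 × ULN is also excluded. The Table 7 cut-off is 177 µmol/L, and 177 / 1.5 = 118, so the entry limit lies at or below the cut-off whenever the laboratory's ULN is 118 µmol/L or less (the ULN is not in the documents). No numeric entry limit is given for eosinophils, WBC, neutrophils, haemoglobin, haematocrit, platelets, GGT, LDH or BUN. Bilirubin enters only through Hy's law at screening.

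Rollover patients are 867 + 675 = 1542 of the planned 1842, or 83.7%. Protocol 4.2.1 screens their laboratory values by investigator judgement alone. Their baseline comes from the pivotal studies, whose entry criteria are not in these documents.

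**3. Whether another planned output separates the cases.** The shift tables in SAP 7.6 use the normal range. Assume the upper normal limit for eosinophils is below 10%. A patient at 11% throughout and a patient who rises from just above normal to 11% then both appear as above-to-above. Mean changes by visit do not identify patients. Listings of PCS patients are planned, but SAP 7.6 does not say that they show baseline values.

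**4. Illustration of size.** The documents give no PCS rate to reproduce; the planned total does add up (867 + 675 + 300 = 1842). Let p be the proportion meeting a criterion at baseline, r the proportion of those who meet it again, and i the true new-onset rate among the rest. All three are assumed.

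Reported rate = p·r + (1 − p)·i. Pre-existing share = p·r / reported rate. Pre-existing patients = 1842·p·r.

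| p | r | i | Reported rate | Pre-existing patients | Share |
|---|---|---|---|---|---|
| 0.5% | 50% | 1% | 0.25% + 0.995% = 1.2% | 4.6 | 20% |
| 1% | 80% | 1% | 0.80% + 0.990% = 1.8% | 14.7 | 45% |
| 3% | 100% | 1% | 3.00% + 0.970% = 4.0% | 55.3 | 76% |
| 0.5% | 50% | 2% | 0.25% + 1.990% = 2.2% | 4.6 | 11% |
| 3% | 100% | 2% | 3.00% + 1.940% = 4.9% | 55.3 | 61% |

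Counting only patients who did not meet the criterion at baseline returns i itself.

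**The case against.** The strongest reply is that the PCS table is a screen and not the endpoint. The laboratory endpoint is change from baseline. SAP 7.6 analyses it directly by visit, with normal-range shifts as well. Protocol 7.3 also turns a result that has worsened significantly from baseline, in medical judgement, into an adverse event, which then enters the SAP 7.3 summaries. No test or decision rule depends on the PCS percentage (SAP 4.4). Protocol 9.7.2 plans to flag changes or values, so absolute cut-offs are within the protocol. All of this stands. It limits the consequence but does not correct the percentage, and none of these outputs separates pre-existing from new cases at the Table 7 cut-offs.

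Three stronger readings are tempting and are not supported:

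- A reader might infer that all chemistry and haematology rows are affected alike. For new patients the entry limits largely remove ALT, AST, ALP and creatinine. Protocol Appendix E mentions enrolled patients with baseline ALT or AST from 2 to 3 × ULN, which must be reconciled with the 1.5 × ULN exclusion, but it does not go above the PCS cut-off.
- A reader might infer that the SAP contradicts itself. Mixing absolute and change-based criteria is a choice, and respiratory rate shows that the mixture is not confined to the laboratory rows.
- A reader might infer that the sponsor will present the percentage as a drug effect. Nothing in the documents says so.

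Uric acid appears in Table 7 but not in Table 6. That is a separate clerical point and adds no weight here.

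**Conclusion.** The point holds in limited form. As written, the SAP 7.6 rule counts patients who met an absolute chemistry or haematology cut-off before any drug, provided that a postbaseline value meets it again. No untreated arm or planned table lets the reader take them out. It matters mainly for the tests without a numeric entry limit in this protocol.

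The size cannot be established. The range of about 1.2% to 4.0% for a true 1% rests wholly on the assumed 0.5% to 3% baseline prevalence and 50% to 100% persistence, and it is not an estimate for any named test. For extreme cut-offs, such as neutrophils at or below 1 × 10⁹/L or platelets at or below 75 × 10⁹/L, the effect may be negligible. This is a reporting defect in the summary of a primary safety domain. It does not invalidate the laboratory analysis.

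**What to change.** In SAP 7.6, keep the all-postbaseline summary and add the following for each chemistry and haematology criterion in Table 7:

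- **(a)** The number and percentage of patients newly meeting the criterion among those who did not meet it in the same direction at baseline, with baseline as in SAP 4.2.
- **(b)** A table of baseline against worst postbaseline status at the Table 7 cut-offs. Low and high limits should be treated separately (WBC ≤3 or ≥20, platelets ≤75 or ≥700, both × 10⁹/L). Baseline and worst postbaseline values should be listed for patients who already met the criterion.

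Replacing the planned summary with (a) alone would be a mistake. It would hide a patient whose GGT goes from 3 to 10 × ULN, and, if direction were ignored, one who crosses from one limit of a two-sided criterion to the other.

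One limit remains. For placebo rollovers the SAP 4.2 baseline precedes the placebo period, so an abnormality that arose on placebo and persisted would still count as new.

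The cost is SAP wording, derived flags from data already collected, a few extra table rows, and denominators that vary slightly by test.
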